The primary efficacy analysis will be conducted when mature response rate data have been observed, which will be determined by the sponsor.

Sensitivity analysis of modified DCR will be carried out in the Efficacy-evaluable Analysis Set.

Phase 2 (Arm C)

ORR is the primary efficacy endpoint in Arm C. ORR of pamiparib combination therapy is assumed as 25% in the study population. The historical rate in a similar population is estimated as 10% (Chen et al 2013)

The null and alternative hypotheses are set as follows:

$$H_0: \text{ORR} = 10\%$$

$$H_a: \text{ORR} > 10\%$$

A binomial exact test will be performed similarly to that described for Arms A and B.

Secondary Efficacy Analysis:

Descriptive statistics will be used to summarize the secondary efficacy analysis.

DCR is defined as the proportion of patients with best overall response (BOR) of CR, PR, or SD. BOR is defined as the best response recorded from the start of study treatment until data cutoff or start of new anti-cancer therapy.

CBR is defined as the proportion of patients with BOR of CR, PR, or durable SD ($SD \geq 24$ weeks).

Exact 95% CIs will be calculated for the rate variables: ORR for patients with measurable disease at baseline, DCR and CBR in the Safety Analysis Set.

PFS is defined as the time from the date of first study treatment to disease progression or death, whichever occurs first.

PFS censoring rule will follow the [FDA Guidance for Industry, Clinical Trial Endpoints for Approval of Cancer Drugs and Biologics \(2007\)](#). Patients who have a clinical determination of progression should undergo an MRI, if possible, to correlate radiographic findings with the clinical findings. Data for patients without disease progression or death at the time of analysis will be censored at the time of the last tumor assessment. Data for patients who are lost to follow-up prior to documented disease progression will be censored at the last tumor assessment date when the patient was known to be progression-free. Data for patients who started new anti-cancer therapy will be censored at the last tumor assessment date prior to the introduction of new therapy. More details will be provided in the statistical analysis plan.

DOR is defined as the time from the date of the earliest documented response to disease progression or death for any cause, whichever occurs earlier. Only responders will be included in the DOR calculation.

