5. STUDY POPULATION

5.1. Inclusion Criteria

Patients must meet all of the following criteria to be eligible for the study:

For all patients

1. Signed Informed Consent Form (ICF)
2. Age ≥ 18 years
3. Histopathologically confirmed glioblastoma (World Health Organization [WHO] Grade IV) ([Louis et al 2016](#))
 - Tumor must have a supratentorial component.
4. 
5. Ability to undergo serial MRI scans (computerized tomography [CT] cannot substitute for MRI)
6. Brain MRI scan ≤ 14 days prior to Day 1
 - Patients requiring glucocorticoids must be on a daily dose equivalent of dexamethasone 4 mg twice daily or less that has been stable for ≥ 7 days prior to the MRI
7. ECOG performance status ≤ 1 ([Appendix 3](#))

8. Ability to swallow whole capsules
9. Adequate hematologic and end-organ function, as defined by the following laboratory results (obtained ≤ 2 weeks prior to Day 1):
 - Absolute neutrophil count (ANC) $\geq 1.5 \times 10^9/L$
 - Platelet count $\geq 100 \times 10^9/L$
 - Hemoglobin ≥ 9 g/dL ≥ 14 days after growth factor support or transfusion if appropriate
 - Serum creatinine $\leq 1.5 \times$ ULN or estimated creatinine clearance ≥ 50 mL/min (calculated using the institutional standard method)
 - Total serum bilirubin $\leq 1.5 \times$ ULN ($\leq 4 \times$ ULN, if Gilbert's syndrome)
 - Aspartate and alanine aminotransferase (AST and ALT) $\leq 3 \times$ ULN
 - Albumin ≥ 3 g/dL
 - International Normalized Ratio (INR) ≤ 1.5 and activated partial thromboplastin time (aPTT) $\leq 1.5 \times$ ULN
10. Female patients of childbearing potential and female partners of male study patients must agree to practice highly effective methods of birth control ([Appendix 4](#)) for the duration of the study, and for ≥ 6 months after last study treatment. In addition, non-sterile male patients must agree to practice highly effective methods of birth control ([Appendix 4](#)) and avoid sperm donation for the duration of the study and for ≥ 6 months after the last dose of study drug.
11. Willingness and ability to comply with all protocol-specified requirements
 - **For patients in Arms A and B (NOT applicable to Arm C)**
 - 12. No previous treatment except surgery (ie, no previous RT, local chemotherapy, or systemic therapy for lower grade central nervous system tumors)
 - 13. Ability to initiate RT ≤ 49 days after surgery, but ≥ 14 days after a biopsy or ≥ 28 days after an open biopsy or a craniotomy with adequate wound healing

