 - 14. Documentation of unmethylated *MGMT* promoter status
 - In escalation cohorts, it is preferable to determine *MGMT* status by quantitative methylation-specific polymerase chain reaction (MS-PCR). Other acceptable platforms include pyrosequencing methodologies and methylation sensitive high-resolution melting (MS-HRM) assays with comparable sensitivity, applied to archival or fresh tumor tissue. Sponsor must be notified prior to utilizing alternate assays or if data from acceptable alternate platforms are available.
 - In expansion cohorts, archival or fresh tumor tissue must be submitted for central analysis of *MGMT* status.

→ For patients in Arm C Escalation (*NOT applicable to Arms A and B*)

15. Documentation of *MGMT* promoter status
 - It is preferable to determine *MGMT* status by MS-PCR. Other acceptable platforms include pyrosequencing methodologies and MS-HRM assays with comparable sensitivity, applied to archival or fresh tumor tissue. Sponsor must be notified prior to utilizing alternate assays or if data from acceptable alternate platforms are available.
16. No prior systemic chemotherapy, other than TMZ, for glioblastoma (including investigational cytotoxic chemotherapy) and no prior anti-angiogenic therapy
 - Prior use of Optune device is allowed with a minimum of 1 week since last Tumor Treating Fields application
17. Histologically confirmed *secondary* glioblastoma will be allowed during the dose escalation phase only
18. Disease that is evaluable or measurable as defined by Response Assessment in Neuro-Oncology (RANO) criteria ([Appendix 2](#))

→ For patients in Arm C Expansion

19. Histologically confirmed *de novo* (primary) glioblastoma with unequivocal first progressive disease (PD) after RT with concurrent/adjuvant TMZ chemotherapy as defined by one or more of the following:
 - PD \geq 3 months after the end of radiotherapy
 - PD that is clearly outside the radiation field
 - PD that has been unequivocally proven by surgery/biopsy
20. Disease that is measurable as defined by RANO criteria ([Appendix 2](#))
 - Patients with recurrent disease must have at least one bi-dimensionally measurable contrast-enhancing lesion with clearly defined margins by MRI scan, with minimal diameters of 10 mm, visible on 2 or more axial slices
21. Documentation of *MGMT* promoter status
 - Tumor tissue (archival or fresh) must be submitted for central analysis of *MGMT* status

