11.2.5.2. Secondary Efficacy Analysis

Descriptive statistics will be used to summarize the secondary efficacy analysis.

DCR is defined as the proportion of patients with best overall response (BOR) of CR, PR, or SD. BOR is defined as the best response recorded from the start of study treatment until data cutoff or start of new anticancer therapy.

CBR is defined as the proportion of patients with BOR of CR, PR, or durable SD (SD \geq 24 weeks).

Exact 95% CIs will be calculated for the rate variables: ORR for patients with measurable disease at baseline, DCR, and CBR in the Safety Analysis Set.

PFS is defined as the time from the date of first study treatment to disease progression or death, whichever occurs first.

PFS censoring rule will follow [FDA Guidance for Industry, Clinical Trial Endpoints for Approval of Cancer Drugs and Biologics \(2007\)](#). Patients who have a clinical determination of progression should undergo an MRI, if possible, to correlate radiographic findings with the clinical findings.

Data for patients without disease progression or death at the time of analysis will be censored at the time of the last tumor assessment. Data for patients who are lost to follow-up prior to documented disease progression will be censored at the last tumor assessment date when the patient was known to be progression-free. Data for patients who started new anticancer therapy will be censored at the last tumor assessment date prior to the introduction of new therapy. More details will be given in the SAP.

DOR is defined as the time from the date of the earliest documented response to disease progression or death for any cause, whichever occurs earlier. Only responders will be included in the DOR calculation.

OS is defined as the time from the date of first study treatment to death of any cause.

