6 STATISTICAL METHODS

6.1 ANALYSIS POPULATIONS

Safety Analysis Set: includes all patients who received any dose of any of the study treatments (pamiparib, RT and/or TMZ). The Safety Analysis Set will be used for efficacy and safety analyses.

Efficacy Analysis Set: includes all patients in the Safety Analysis Set who:

Arms A & B: had a tumor assessment at baseline and at End of Treatment unless discontinued treatment or study early due to disease progression or death prior to tumor assessment.

Arm C: had measurable disease at baseline and at least one postbaseline tumor assessment unless discontinued treatment or study early due to disease progression or death prior to tumor assessment.

DLT-Evaluable Analysis Set: includes patients from escalation cohorts only in the Safety Analysis Set who received ≥ 42 Gy of RT (Arms A and B) and $\geq 70\%$ of scheduled pamiparib (Arms A, B and C) and TMZ (Arms B and C) during the DLT assessment window. All patients who had a DLT event will be considered DLT-evaluable regardless of study treatment intensity.

PK Analysis Set: includes all patients for whom valid pamiparib PK parameters can be estimated.

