6.4.2 Secondary Efficacy Endpoints

Disease Control Rate (DCR – for arm C)

DCR is defined as the proportion of patients with best overall response of CR, PR or SD per RANO criteria. CR or PR will be confirmed by a subsequent tumor assessment at least four weeks apart. DCR will be performed in similar fashion as described in primary endpoint modified DCR on Efficacy Analysis Set.

Objective Response Rate (ORR – for arm A&B)

ORR for arm A&B will be performed for Efficacy Analysis Set in similar fashion as in primary endpoint for arm C.

Progression-Free Survival (PFS)

PFS is defined as the time from the first dose date to disease progression per RANO criteria or death, whichever occurs first. PFS analysis will be performed for all arms using Safety Analysis Set.

PFS censoring rule will follow FDA *Guidance for Industry, Clinical Trial Endpoints for Approval of Cancer drugs and Biologics* (2007). The censoring rules are described in Table 1. If a patient meets the criteria for more than 1 censoring rule, PFS will be censored at the earliest censoring date.

Table 1 Censoring Rules for Analysis of Progression-Free Survival

Censoring Categories	Date of Progression or Censoring	Outcome
Progression documented on scheduled visit or between scheduled visits	Date of first PD assessment	Progressed
Death before first tumor assessment	Date of death	Progressed
Death between scheduled adequate assessment visits	Date of death	Progressed
No baseline or postbaseline tumor assessments	Date of the first dose	Censored
No PD or death at the time of data cut-off or withdrawal from study	Date of last adequate radiologic tumor assessment prior to or on date of data cut-off or withdrawal from study	Censored

New anticancer treatment started	Date of last adequate radiologic tumor assessment prior to or on date of new anticancer treatment	Censored
Death or PD immediately after two or more missed visits	Date of last adequate radiologic tumor assessment before missed tumor assessments	Censored

CR = complete response, PD = progressive disease, PR = partial response, SD = stable disease
Adequate tumor assessment is a radiologic assessment of CR, PR, SD, non-CR/non-PD or PD as determined by investigators.

Duration of Response (DOR)

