8 CHANGES IN THE PROTOCOL PLANNED ANALYSIS

1. Sample size reduction: The overall sample size was reduced during the study since the expansion cohorts were considered too large for this non-randomized and non-registrational study.
2. All arm B expansion cohort related analysis and language are removed since it was decided not to enroll expansion cohort for arm B

3. Primary analysis will be performed on efficacy analysis set, not safety analysis set. No sensitivity analysis will be performed.

4. Exploratory objectives and endpoints in the protocol will not be explored in this SAP

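### The SAP's ORR denominator for Arms A and B departs from the protocol (no measurable-disease condition, different analysis set) without listing it; the net effect on the rate is unknown

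*SAP*

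**What the plan says.** **Protocol.** Section 11.2.5.2 plans exact 95% confidence intervals for "ORR for patients with measurable disease at baseline, DCR, and CBR in the Safety Analysis Set". The synopsis says the same. Neither limits the rule to one arm. Section 11.2.1 assigns all efficacy analyses to the Safety Analysis Set, and section 11.2.5.2 uses the efficacy-evaluable set for sensitivity analyses.

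**SAP.** Section 6.4.2 says "ORR for arm A&B will be performed for Efficacy Analysis Set in similar fashion as in primary endpoint for arm C". Section 6.1 defines the Efficacy Analysis Set separately by arm:

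- Arms A and B: patients who "had a tumor assessment at baseline and at End of Treatment unless discontinued treatment or study early due to disease progression or death" before the assessment.
- Arm C: patients who "had measurable disease at baseline and at least one postbaseline tumor assessment", with the same kind of exception.

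Only the Arm C branch mentions measurable disease. In section 8, the one item on analysis sets reads "Primary analysis will be performed on efficacy analysis set, not safety analysis set. No sensitivity analysis will be performed". No item there mentions secondary ORR or measurable disease.

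**Population.** Arms A and B enrol newly diagnosed patients under the criterion "No previous treatment except surgery" (Protocol 5.1). The criterion "Disease that is measurable as defined by RANO criteria" appears there for the Arm C expansion. SAP 6.4.3 plans a complete-resection subgroup for modified DCR in Arms A and B.

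**The concern.** ORR is a secondary endpoint for Arm A in Phase 2 and for Arms A and B in Phase 1b. Someone who knows the protocol would take the denominator to be treated patients with measurable disease. The SAP's specific sentence gives a different one, in two respects.

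First, patients with no measurable lesion after surgery enter the denominator. Under Protocol Appendix Table 5, a target-lesion partial response needs a fall of at least 50% in the sum of products of diameters (SPD) of the target lesions. A patient with no target lesion cannot have one. Patients with only small enhancing foci could respond through the non-target criteria alone. Patients with no enhancing lesion are coded not applicable, and the documents do not state how that code maps to best overall response.

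Second, treated patients without an EOT scan leave the denominator unless progression or death explains the gap. Under SAP 6.2.1, patients with no postbaseline assessment count as non-responders for ORR. Removing them from the set cancels that rule for those who also lack an excepted reason.

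Neither departure is listed as a change, so two analysts working from these documents could report different ORRs for the same arm.

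**Working it through.** The documents give no ORR assumption, power or precision figure for Arms A and B, so there is no stated figure to reproduce. The check compares the text and then illustrates how each departure moves the rate.

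**Text comparison, Arms A and B ORR**

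| Feature | Protocol 11.2.5.2 | SAP 6.4.2 with 6.1 | Listed in SAP 8? |
|---|---|---|---|
| Analysis set | Safety | Efficacy | No (primary analysis only) |
| Measurable disease at baseline | Required | Not required | No |
| EOT scan | Not required | Required, except after progression or death | No |

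**Inputs**

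- From the documents: n = 40 in the Arm A expansion cohort (SAP section 5).
- Assumed, not in the documents: the share f of patients without measurable disease, an ORR of 25% in measurable patients, and the number d excluded for no EOT scan.
- Starting assumptions: no responses in non-measurable patients, and only non-responders excluded.

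**Formulas**

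- Responders: R = 0.25 × 40(1 − f).
- Protocol rule: R / [40(1 − f)].
- SAP rule: R / (40 − d).
- Exact (Clopper-Pearson) 95% limits for x of n: the 2.5% quantile of Beta(x, n − x + 1) and the 97.5% quantile of Beta(x + 1, n − x).

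**Effect of dropping the measurable-disease condition**

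| f | Protocol rule (95% CI) | SAP rule, d = 0 (95% CI) | SAP rule, d = 4 (95% CI) |
|---|---|---|---|
| 20% | 8/32 = 25% (11.5 to 43.4) | 8/40 = 20% (9.1 to 35.6) | 8/36 = 22.2% (10.1 to 39.2) |
| 40% | 6/24 = 25% (9.8 to 46.7) | 6/40 = 15% (5.7 to 29.8) | 6/36 = 16.7% (6.4 to 32.8) |
| 50% | 5/20 = 25% (8.7 to 49.1) | 5/40 = 12.5% (4.2 to 26.8) | 5/36 = 13.9% (4.7 to 29.5) |

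**Effect of the EOT-scan condition**

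- With f = 0, the protocol rule gives 10/40 = 25%. The SAP rule gives 10/36 = 27.8% at d = 4 and 10/32 = 31.25% at d = 8.
- With f = 10%, the protocol rule gives 9/36 = 25%. The SAP rule at d = 6 gives 9/34 = 26.5%.

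**Break-even.** The SAP rate is below the protocol rate when 40 − d > 40(1− f), that is, when d < 40f. It is above when d > 40f. For f = 20%, 40% and 50% the break-even is d = 8, 16 and 20; for f = 10% it is d = 4.

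**Non-target responses.** At f = 40% and d = 0, let k of the 16 non-measurable patients respond through the non-target criteria. The SAP rate is (6 + k)/40: 15% at k = 0, 20% at k = 2 and 25% at k = 4. The two rules agree at k = 4, which is 25% of 16.

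**The case against.** Four points deserve weight.

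1. **The SAP may not mean what 6.4.2 appears to say.** Its reference to the Arm C primary analysis could be read as importing Arm C's measurable-disease condition. SAP 6.1 also says the Safety Analysis Set serves efficacy analyses, and 6.4.1 says efficacy analysis covers every patient in every arm. The specific sentence names the set, and 6.1 defines that set by arm, so the reading used here is the better one. The ambiguity is real, though, and is itself a reason to state one denominator. Neither general statement restores the measurable-disease condition.

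2. **The new set is not hidden.** It is named in 6.4.2 and defined in 6.1. The section 8 item could also be taken to contrast the main analysis with sensitivity analyses, which would cover more than the primary endpoint. That reading is weakened because PFS and OS stay on the Safety Analysis Set, and it would still leave the measurable-disease condition unlisted. A reader might infer concealment; the documents show only an incomplete change list.

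3. **The set change is wider than this endpoint.** SAP 6.4.2 also moves Arm C DCR to the Efficacy Analysis Set, where the protocol has the Safety Analysis Set. This is correct. The dropped measurable-disease condition is the part specific to Arms A and B.

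4. **The practical effect is not documented.** A planned complete-resection subgroup gives no count and does not prove that those patients lack measurable disease. One inclusion criterion for all patients is not visible in the public text. It is unlikely to concern measurability, because separate Arm C criteria cover that, but it cannot be checked.

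**Conclusion.** The mismatch stands. The protocol's ORR denominator and the SAP's denominator for Arms A and B differ in analysis set and in the measurable-disease condition. Section 8 records neither difference, and the SAP's general statements do not agree with its specific one.

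A reader might infer that the SAP rule dilutes ORR. The documents do not support a fixed direction. Including patients with no target lesion tends to lower the rate; excluding non-responders without an EOT scan raises it. Which effect is larger depends on the non-measurable share, the number excluded and any non-target responses, and the documents give none of these. The percentages above are illustrations only.

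The consequence is limited. ORR in Arms A and B is secondary and descriptive, no decision rule uses it, and modified DCR is unaffected. This is a point to consider, not a threat to the main result. Confidence is high that the texts differ, and lower about which population would in fact be analysed.

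**What to change.** **Preferred.** In SAP 6.4.2, analyse ORR for Arms A and B in Safety Analysis Set patients with measurable disease at baseline, as Protocol 11.2.5.2 plans, and report that denominator. No section 8 entry is then needed for this endpoint. Label any Efficacy Analysis Set or all-patient rate as supplementary.

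**Alternative.** If the sponsor keeps the Efficacy Analysis Set as the main denominator, list both the dropped measurable-disease condition and the move from the Safety to the Efficacy Analysis Set in section 8. State as well how best response is coded for patients with no enhancing disease at baseline.

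Under either choice, bring the general statements in SAP 6.1 and 6.4.1 into line with 6.4.2. DOR, which covers responders only, and the modified DCR analysis need no change for this point.

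**Cost.** The preferred change takes one sentence in the SAP and a flag derived from baseline lesion data already collected. The denominator shrinks and the interval widens. In the 40% illustration the exact 95% interval runs from 9.8% to 46.7% for 6/24 (36.9 points), against 5.7% to 29.8% for 6/40 (24.1 points).

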8.3. Tumor Assessments

8.3.1. Magnetic Resonance Imaging (MRI)

Tumor assessments will include all known or suspected disease sites. The minimum recommended MRI sequences include: (i) parameter-matched precontrast and post-contrast inversion recovery-prepared, isotropic 3D T1-weighted gradient-recalled echo; (ii) axial 2D T2-weighted turbo spin-echo acquired after contrast injection and before post-contrast 3D T1-weighted images to control timing of images after contrast administration; (iii) precontrast, axial 2D T2-weighted

fluid-attenuated inversion recovery; and (iv) precontrast, axial 2D, 3-directional diffusion-weighted images. MRIs will be performed at screening (within 14 days of Day 1) and every 8 weeks (± 7 days), unless otherwise specified in [Appendix 1](#).

Non-contrast cranial MRI may only be used to document disease in those patients who are allergic to contrast. Tumor assessments should be repeated at the end of treatment visit if more than 4 weeks have passed since the last evaluation.

The same imaging technique used at screening should be used throughout the study.

Anti-tumor activity will be assessed through radiologic tumor assessments conducted at screening, during treatment as specified in the Schedule of Activity, whenever disease progression is suspected (eg, symptomatic deterioration), and at the time of withdrawal from treatment (if not done in the previous 4 weeks). All patients' files and radiologic images (in Digital Imaging and Communications in Medicine [DICOM] format) must be available for source verification and for central review.

Assessment of response will be made using the RANO criteria ([Appendix 2](#)). Responses should be confirmed with two assessments at least 4 weeks apart. Efficacy evaluations using the RANO criteria involve post-contrast MRI findings, non-contrast T1 and T2 FLAIR images, use of corticosteroid dose, and clinical status per RANO ([Ellingson et al 2015](#)).

Following initial evidence of radiographic progressions and due to the potential for pseudo-progression patients may, at the discretion of the investigator, remain on treatment until further imaging is performed 4 to 8 weeks (at the discretion of the investigator) after the initial determination of potential progression.

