At each evaluation, a time point response is to be determined for target lesions, non-target lesions, and new lesion. The RANO criteria and associated conventions for each post-treatment time point assessment are provided in [Appendix Table 5](#). Overall time point response is derived as described in [Appendix Table 6](#).

Unless progression is observed, overall response can only be determined when all lesions are assessed.

3. Confirmation

Confirmation assessments for overall time point responses of complete response (CR) and partial response (PR) are to be performed no less than 4 but no more than 8 weeks after the initial time point at which a response is seen.

4. Best Response

Best response, incorporating confirmation requirements, will be derived from the series of time point responses and need not be considered when assigning response at each time point.

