CBR (clinical benefit rate) is defined as the proportion of patients with best overall response of CR, PR or SD \geq 24 weeks per RANO criteria. CR or PR will be confirmed by a subsequent tumor assessment at least four weeks apart.

BOR (best of response) is defined as the best response recorded from the start of study treatment until data cutoff, or start of new anti-cancer therapy. Computation of BOR will consider timepoints prior to PD when determining BOR.

Time to event data

OS (overall survival) is defined as the time from the first dose date to date of death for any cause. Patients that are still alive at the time of analysis will be censored at the last contact date that is known to be alive.

PFS (progression free survival) is defined as the time from the first dose date to disease progression per RANO criteria or death, whichever occurs first. Censoring rules for PFS are described in Table 1 in [section 6.4.2](#).

DOR (duration of response) is defined as the time from the date of the earliest documented response to disease progression or death for any cause whichever occurs earlier.

All calculations and analyses will be conducted using SAS version 9.4 or higher.

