6.4.1 Primary Efficacy Endpoints

Efficacy analysis will be performed on all patients for all arms. For Arm A and Arm C, phase 1b and phase 2 are presented in different table columns.

Arm A and Arm B

Modified Disease Control Rate is the primary efficacy endpoint in Arms A and B. It is defined as the proportion of patients with CR, PR or SD per RANO criteria as the response assessment at the end-of-treatment (EOT) visit, as scheduled per protocol. Patients with no EOT tumor assessment, as scheduled per protocol (due to any reason), will be considered non-responders for modified DCR. Modified DCR of Pamiparib combination therapy is assumed as 60% in the study population. The historical rate in a similar population is estimated as 40% (Rivera et al., 2010). No formal hypothesis testing will be performed. Two-sided binomial exact 80% and 95% CI of modified DCR will be constructed to assess the precision of the rate estimate.

Arm C

Objective Response Rate (ORR) is the primary efficacy endpoint in arm C. The analysis will be performed for the efficacy analysis set. It is defined as proportion of patients with best overall response of CR or PR per RANO criteria (confirmed by a subsequent tumor assessment at least four weeks apart). Best overall response will be assessed from the start of study treatment until data cut-off date, disease progression or start of new anti-cancer therapy. Patients without postbaseline tumor assessment is considered nonresponders. ORR of Pamiparib combination therapy is assumed as 25% in the study population. The historical rate in a similar population is

estimated as 10% (Chen et al, 2013). Two-sided binomial exact 80% and 95% CI of ORR will be constructed to assess the precision of the rate estimate.

In addition, the number (%) of the best overall response categories (CR, PR, SD, PD) will be presented.

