DOR is defined as the time from the date of the earliest documented response (confirmed or unconfirmed) of CR or PR to disease progression or death for any cause, whichever occurs earlier. Only responders will be included in the DOR analysis. Censoring rule for DOR will follow PFS censoring rule.

Overall Survival (OS)

OS is defined as the time from the date of first study treatment to death of any cause. Patients who have not died by the analysis cutoff date will be censored at the last date known to be alive or the data cutoff date, whichever is earlier. OS will be performed for Safety Analysis Set.

Time-to-event variables PFS, OS and DOR will be estimated using the Kaplan-Meier (KM) method. KM estimates of PFS, DOR and OS will be plotted over time. Median PFS, DOR and OS, if possible to estimate, in each arm will be presented, along with their 2-sided 95% CIs using Brookmeyer and Crowley method (Brookmeyer & Crowley, 1982). The PFS-6m, PFS-12m, OS-6m, and OS-12m, defined as the proportion of patients in the Safety Analysis Set who remain alive and progression-free at 6 months and 12 months (or alive at 6 month and 12 months for OS), will be estimated using KM method along with the corresponding 95% confidence interval constructed using Greenwood's formula (Greenwood, 1926).

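### SAP 6.4.2 lets duration of response start at an unconfirmed CR or PR and does not tie the word responder to the confirmed-response ORR, so both the DOR patient set and the start date are open to two readings

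*SAP*

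**What the plan says.** **ORR.** SAP 6.4.1 (Arm C, primary) counts a best overall response of CR or PR only when it is "confirmed by a subsequent tumor assessment at least four weeks apart"; SAP 6.2.1 says the same. For Arms A and B, SAP 6.4.2 states that "ORR for arm A&B will be performed for Efficacy Analysis Set in similar fashion as in primary endpoint for arm C". The protocol agrees. Section 8.3.1 says "Responses should be confirmed with two assessments at least 4 weeks apart", and Appendix 2 says "Best response, incorporating confirmation requirements, will be derived from the series of time point responses".

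**DOR.** SAP 6.4.2 starts the clock at the "earliest documented response (confirmed or unconfirmed) of CR or PR" and ends it at progression or death. The next sentence is "Only responders will be included in the DOR analysis". DOR censoring follows the PFS rules in SAP Table 1.

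**DOR elsewhere.** SAP 6.2.1 has "DOR (duration of response) is defined as the time from the date of the earliest documented response", with nothing about confirmation. Protocol 11.2.5.2 is also silent on confirmation and adds "Only responders will be included in the DOR calculation". The parenthesis in SAP 6.4.2 is therefore new, and SAP section 8, which lists changes from the protocol's planned analysis, does not mention it.

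**The concern.** DOR is normally read next to ORR: so many patients responded, and their responses lasted so long. That works only if both describe the same patients. Here ORR requires confirmation, while the DOR sentence expressly admits a response without it. The word that should set the DOR population, responders, is not defined there. Two programmers could follow the text faithfully and build different DOR datasets, with different patients, different start dates or both. With very few responders expected, one or two patients are enough to move the result.

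**Working it through.** **1. Figures in the plan.** The documents state no planned or assumed DOR. The nearest stated figure is the Arm C threshold of 6 of 30 in SAP section 5. It reproduces: the 80% exact interval for 6/30 is 10.9% to 32.5%, which excludes 10%, and for 5/30 the lower bound is 8.3%, which does not. It does not depend on how DOR is defined. Expected responders in the Arm C expansion are 0.25 × 30 = 7.5, so about 7.

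**2. The two readings applied to scan sequences.** Scans are 8-weekly (Protocol 8.3.1).

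- Reading 1: a responder is anyone with a documented CR or PR.
- Reading 2: a responder is an ORR responder, and the parenthesis only sets the start date.

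| Scan sequence | ORR | DOR, reading 1 | DOR, reading 2 |
|---|---|---|---|
| PR, PR | responder | in, from scan 1 | in, from scan 1 |
| PR, PD | non-responder | in, event at about 8 weeks | out |
| PR, no later scan, alive | non-responder | in, censored at the response scan | out |
| PR, SD, PR, PR | responder | in, from scan 1 | in, from scan 1 |

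Rows 2 and 3 show ORR non-responders entering DOR on reading 1.

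Row 4 shows that reading 2 does not fully repair the rule. Such a sequence can occur, because Appendix Table 5 of the protocol downgrades a PR to SD when the glucocorticoid dose has risen. Protocol Appendix 2 wants confirmation 4 to 8 weeks after the initial response. The PR at scan 1 is next repeated at scan 3, 16 weeks later, so scan 1 is unconfirmed and the confirmed response starts at scan 3. Starting at scan 1 adds 16 weeks (112 / 30.4375 = 3.7 months). The SAP gives only a minimum gap, so an analyst could also argue that scan 3 confirms scan 1, and the text does not settle it.

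**3. Illustration with assumed durations.** Take seven confirmed responders at 4, 6, 8, 10, 12, 14 and 16 months, all progressing. The median is the 4th value, 10 months. An 8-week interval is 56 / 30.4375 = 1.8 months.

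- Add two unconfirmed responders who progress at the next scan: 1.8, 1.8, 4, 6, 8, 10, 12, 14, 16. The median is the 5th value, 8 months.
- Add two unconfirmed responders with no later scan. SAP Table 1 censors them at the last adequate assessment, which is the response scan itself. They leave the risk set before any event, and the median stays at 10 months.

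**4. Range for the progress-at-next-scan case.** Assume that confirmed responders have DOR of at least 8 weeks with an exponential tail and true median M, and that a fraction u of the DOR set is unconfirmed and fails at 8 weeks. Then beyond 8 weeks S(t) = (1 − u) × exp(−λ(t − 8)), with λ = ln 2 / (M − 8). Setting S(t) = 0.5 gives

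median = 8 + (M − 8) × ln(2(1 − u)) / ln 2.

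| True M (weeks) | u = 10% | 20% | 30% | 40% |
|---|---|---|---|---|
| 16 | 14.8 | 13.4 | 11.9 | 10.1 |
| 24 | 21.6 | 18.8 | 15.8 | 12.2 |
| 40 | 35.1 | 29.7 | 23.5 | 16.4 |

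One unconfirmed patient added to seven confirmed is u = 1/8 = 12.5%, and two is u = 2/9 = 22%. Those cases lie between the 10% and 30% columns. With DOR limited to confirmed responders, the median is M.

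**The case against.** The strongest reply is that the parenthesis describes the start date, while the next sentence sets the population. Read together, ORR responders enter and their clock starts at the first CR or PR scan rather than the confirming one, which is standard. There is support for this. The ORR definition, which requires confirmation, uses non-responder without a qualifier, whereas the modified DCR definition says which endpoint it means. The protocol builds confirmation into best response. The protocol and SAP 6.2.1 define DOR without the parenthesis.

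This reading is coherent and may be what was intended, so entry of ORR non-responders into DOR is possible but not established. The reply does not close the point. The SAP never says that a DOR responder is an ORR responder, and a response that is later confirmed would not usually be called unconfirmed. Row 4 of the first table also shows the start date going wrong on this reading.

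A reader might infer something stronger: that the sponsor chose to include unconfirmed responders, or that reported DOR will be biased downwards. The documents support neither. No rationale is given and SAP section 8 records no such change. The direction is not fixed either: early progressors tend to lower the median, immediate censoring adds almost no follow-up, and an early clock start lengthens DOR.

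**Conclusion.** The point holds as a defect in the written rule. SAP 6.4.2 admits unconfirmed responses into the DOR definition and leaves responder undefined. One permitted reading breaks the match between DOR and ORR, and the other can still misplace the start date. With about 7 responders expected in the Arm C expansion, one or two patients could alter the Kaplan-Meier estimate.

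The size cannot be established from the documents. The shift from 10 to 8 months and the tabulated medians rest on assumed durations, assumed numbers of unconfirmed responders and progression at the very next scan.

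The importance is minor. DOR is a secondary, descriptive endpoint with no test, threshold or decision attached, the SAP describes the study as non-randomised and non-registrational, and the primary endpoints (ORR in Arm C, modified DCR in Arm A) are untouched.

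**What to change.** Replace the DOR sentence in SAP 6.4.2 with: *DOR is analysed in patients with a confirmed CR or PR (the ORR responders), from the date of the first scan showing the response that was later confirmed, to PD or death.* Make SAP 6.2.1 match. If a version that includes unconfirmed responses is wanted, label it as such and report it separately.

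The same edit should name the analysis set. SAP 6.4.2 gives none for DOR, the protocol uses the Safety Analysis Set, and the SAP analyses ORR in the Efficacy Analysis Set.

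The cost is one sentence and its cross-reference, with no new data. It should be settled before the DOR programs are run.
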